22 significant resources to achieve its target. As part of the main objectives of telehealth
23 technology, we believe that our suggested approach will limit not only the number but
24 also the frequency of VNS. In addition it may even supersede VNS as it provides to some
25 extent more continuous and more objectives measures to provide a better follow up to our
26 patients after discharge.

27
28 In conclusion, it seems reasonable to believe that monitoring using telehealth
29 technology and managing the general health care patients receive after a hospital vascular
30 ARGI intervention will improve overall health, patient care and will reduce post
31 operative complications. Our project will be conducted to directly give more and
32 continuous attention to postoperative period after hospital discharge. We believe that
33 early readmission is a “failed discharge” as has suggested by others. This matter is of
34 great interest particularly to our specialty.

35 36 37 **Objectives**

38 The primary objective of the current project is to compare outcomes for patients
39 who receive post discharge health care monitoring (which includes using Telehealth
40 electronic monitoring; THEM) to patients who receive standard of care (SOC) and routine
41 discharge instructions and no monitoring.

42 **Outcomes**

43 The primary outcomes include 30-day readmissions, post-operative complications
44 and access site/wound infections. Secondary outcomes will include a pre and post
45 surgery quality of life measures (SF-8) and patient satisfaction (>30-day) along with an
46 occurrence of any 30-day stroke, MI or death.

1
2
3 **Study hypotheses:**
4

- 5 1. A smaller percentage of THEM patients will require a 30-day unplanned
6 readmission.
7 2. A smaller percentage of THEM patients will develop a SSI.
8 3. THEM patients will report greater post discharge satisfaction and higher
9 quality of life measures.

10
11 **Significance:**
12

- 13 1. Information and results obtained from this study may suggest additional post
14 discharge treatment approaches which in turn could lower 30-day
15 readmissions and complications for patients undergoing surgery.
16
17 2. Likewise, information and results obtained from this study could be used to
18 help promote greater patient satisfaction and quality of life measures.
19
20 3. This approach may impact some direct cost pertaining to post-discharge
21 follow-up as visiting nurse services. THEM approach will provide a direct,

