22 measurable, specific tool to provide therapy related information to the treating
23 physician during post-discharge period.
24

25
26 **Study Design:**
27

28 The current study is designed to be a **prospective, randomized, open-label, single-**
29 **center with blinded endpoints (PROBE) study.**¹⁴ More specifically, it is designed to test
30 the hypothesis that Tele-health monitoring will decrease 30-day readmission and
31 complication rates. Patients with planned vascular ARGIs will be consented for possible
32 inclusion. Patients who give their consent will be enrolled and randomly assigned to one
33 of the two treatment arms: 1) standard of care (SOC) or 2) Tele-health electronic
34 monitoring (THEM) using TeleMed 2020 home health monitoring system.
35 The primary endpoints will be measured as simply the occurrence or not of any
36 unplanned 30-day readmission and/or complication (0/1). Patients in the intervention
37 group (THEM) will receive a tablet computer and home monitoring medical devices with
38 sensors to transmit the information to a central website that will be monitored by care
39 managers. Medical devices will include weight scales, blood pressure cuffs and oxygen
40 saturation monitors. Clinical care managers will remotely monitor the patients and all
41 electronic readings. Clinical care managers will call or send electronic messages to the
42 patients based on alerts generated by the tele-health monitoring system.
43

44 **Sample:**

1
2 The population for this study will be patients with any planned vascular procedures with
3 cut-down access to the groin and will be treated by one of the Vascular Surgeons in the
4 Vascular Center of Excellence (VCOE).

5
6 *Sample Size:*

7 The sample size was estimated based on the readmission rates from a previous research
8 study. An overall sample size of 200 subjects will have 80% power to detect a reduction
9 in the 30-day infection/readmission rate from ~12 in the SOC group to ~2% in the THEM
10 group using a 2-sided α of 0.05. We expect a 10% drop-out rate and thus plan to enroll
11 110 patients in each group (N=220 overall).

12
13
14 *Inclusion/exclusion criteria:*

15 Patients meeting the inclusion criteria, which is any planned vascular procedures with
16 cut-down access to the groin and treated by one of the Vascular Surgeons in the Vascular
17 Center (VCOE) will be consented and enrolled. Patients will be excluded for any of the

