11 sharing of critical information yielding earlier and more active care plan management.

12 The company is based in Indianapolis, Indiana.

13
14 <http://www.bloomberg.com/research/stocks/private/snapshot.asp?privcapid=310873357>

15
16
17 For the THEM group, the care manager will:

- 18
19 1. Monitor patient vital signs: daily weight, blood pressure, pulse, , oxygen
20 saturation and temperature
- 21 2. Ask about the description of the postoperative wound site: including any
22 surrounding erythema, discharge, wound dehiscence and healing. If necessary,
23 ask for a picture of the wound site to be sent. A transmitted photograph of the
24 wound condition may augment amount of knowledge available to clinical care
25 management team.
- 26 3. Complete a target organ evaluation: which means to evaluate the bypass and this
27 will include general feeling, pain (location, degree, type and relieving elements).
- 28 4. Assess compliance with the discharge medications.

29
30
31 Early signs of infection would include, but not be limited to fever, tachycardia,
32 discharge, erythema, wound dehiscence, and pain. All of these will be evaluated via
33 telecommunication tools by the care manager and if needed immediately discussed with
34 supervising physician. In addition, the patient, if needed, will be scheduled for an early
35 office visit and/or re-hospitalization.

36
37 For the SOC group, the care manager will follow the current standard of care.

38 39 40 **Procedure:**

41 **PRE-TREATMENT:**

- 42 • Patients will be identified by the Vascular Surgeon and scheduled for the
43 procedure.
- 44 • Study coordinator will review patient scheduling records to identify
45 potential study participants.

- The study coordinator will explain the research study and the informed consent with the patient prior to the surgical intervention.
- The patient upon appropriate consent signs and dates the consent form and the HIPPA authorization form, which is attached to the consent form.
- Patient upon informed consent is randomized to either receive the treatment (THEM) or to the SOC control group (SOC).
- Complete a pre-treatment SF-8 and baseline history form.

Quality of life measure

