The SF-8™ Health Survey is a brief and comprehensive quality of life population survey. It has only eight questionnaire items, and by design according to the company’s website “was constructed to replace the SF-36® and SF-12® in population health surveys in the U.S. and internationally. Accordingly, it has been translated and linguistically validated for use in more than 30 countries and languages using IQOLA Project methods. It has been adopted by federal agencies (e.g., the DOD), leading polling organizations (e.g., the Roper-Starch Worldwide Health Report), and industry sponsors of clinical trials and effectiveness research (e.g., Glaxo Smith Kline, Johnson & Johnson, and Searle).” In addition, the validation and norming measures of the SF-8™ Health included the general population as well as many subgroups of subjects with co-morbidities such as depression and diabetes. The SF-8™ is a very sensitive test that has both test/retest reliability as well as the ability to detect change of time. The scoring of the SF-8™ produces two summary scores. One for the physical (PCS) and one for the mental dimension (MCS). It also provides the same 8 subscale scores for each dimension as the SF-36.

Vascular Intervention:

All patients will receive their planned and scheduled procedures.

Follow-Up Protocol:

After 2-4 weeks, all patients will have a follow-up visit scheduled at the VCOE clinic. Follow-up will include physical exam including a routine visual inspection of access site wound and comments will be collected. All patients will complete a second SF-8 survey form and a patient satisfaction survey. If follow-up visit is less than 30 days, then a member of the study team will call patients and obtain SF-8, satisfaction survey and follow-up form.

Data Collection:

Will include (see appendix):

- 1) Signed consent forms
- 2) Enrollment and demographics form
- 3) SF-8 survey
- 4) Patient satisfaction survey
- 5) 4 week follow-up form

Schedule of Events

Information:	SOC	THEM
Sign Informed Consent	Pre-Intervention	Pre-Intervention
Randomization	Pre-Intervention	Pre-Intervention
Pre-treatment	SF-8 survey	SF-8 survey
Equipment & instructions	At discharge	At discharge
Follow Up:		
Special issue follow-up	Patient initiated	Patient or monitor initiated
Routine follow-up exam	2-4 weeks	2-4 weeks
	SF-8 survey	SF-8 survey
	Satisfaction survey Follow-up form Debriefing	Satisfaction survey Follow-up form Debriefing

1
2
3
4
5
6
7
8
9
10
11
12
13
14
15
16
17
18
19
20
21

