22
23
24
25
26
27
28
29
30
31

SOC = Standard of Care
THEM = Tele-Health Electronic Monitoring

Statistical Analysis:

All analyses will be based on intention-to-treat (ITT) analyses. However, if possible we will sub-analyze the data on a per-protocol basis as well. Descriptive statistics will be expressed in terms of frequencies, percentages, or means \pm standard deviation (SD). Categorical variables will be tested by chi-square or Fisher exact tests and continuous variables will be tested by student t-test or paired t-test for pre/post measures, where deemed appropriate. Survival and freedom from event curves such as freedom from re-admission will be created using the Kaplan Meier method, compared by the Log Rank test, and graphically presented using life tables. All probability values will be 2 sided and ‘p’ values <0.05 will be considered significant. Statistical analyses will be performed using SPSS version 19.0 for Windows. This study will be registered at ClinicalTrials.gov.

End Points:

The primary outcomes include 30-day readmissions, post-operative complications and access site/wound infections.

Secondary outcomes will include a pre and post-surgery quality of life measures (SF-8), patient satisfaction (>30-day) and number of VNS visits along with an occurrence of any 30-day stroke, MI or death.

Definitions:

1
2 Event-free survival will be defined as the freedom from unplanned 30-day
3 readmission and/or 30-day access site wound infection.

4
5 **Human Subjects**

6 **Recruitment Method(s)**

7
8 The current study protocol received approval from our local institutional review
9 board. The study group participants will sign consent papers on admission to the
10 vascular lab when the patient presents for pre-procedure evaluation. The study care
11 manger will identify potential study participants, and provide information about the
12 study. Study staff will be trained and knowledgeable on the research protocol. This
13 study will not offer any direct benefit for the study participants. Staff will not begin
14 consenting patients until they have completed this training and are in compliance with
15 any pertinent trainings offered by Research and Grants.

16
17 **Payment/Costs of Testing:**

18
19 Patients enrolled in both study comparison groups (THEM and SOC) will not
20 incur additional expenses as a due to their participation in this study. Normal standard of

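### SF-8 part of hypothesis 3: a baseline-adjusted comparison of the arms would use the baseline score better than the planned t-tests, provided that baseline is completed before allocation is disclosed

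*Combined protocol and SAP*

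**What the plan says.** All references are to the combined protocol and SAP.

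- **Study hypotheses.** The third states that "THEM patients will report greater post discharge satisfaction and higher" quality of life. This compares THEM with SOC. The Outcomes and End Points sections list SF-8, before and after surgery, as a secondary outcome.
- **Procedure, PRE-TREATMENT.** One item reads "Patient upon informed consent is randomized to either receive the treatment" or to the control group; the item after it reads "Complete a pre-treatment SF-8 and baseline history form". The Schedule of Events also lists randomization above the pre-treatment SF-8. Neither gives times. Study Design describes the trial as open-label. The Randomization section has the equipment or the usual instructions handed over after the procedure and before discharge. No section says when the patient is told the arm.
- **Quality of life measure.** SF-8 yields a physical (PCS) and a mental (MCS) summary score, and eight subscales.
- **Follow-Up Protocol.** A clinic visit takes place after 2-4 weeks, and "All patients will complete a second SF-8 survey form and a patient satisfaction survey". Then: "If follow-up visit is less than 30 days, then a member of the study team will call patients and obtain SF-8", with the satisfaction survey and the follow-up form. The Schedule of Events shows one follow-up SF-8.
- **Statistical Analysis.** "continuous variables will be tested by student t-test or paired t-test for pre/post measures, where deemed appropriate". No section mentions ANCOVA, regression or any other baseline adjustment.
- **Sample Size.** "An overall sample size of 200 subjects will have 80% power to detect a reduction" in the infection/readmission rate, from about 12% to about 2%. There is no power statement for SF-8.

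**The concern.** The analysis sentence attaches the paired t-test to pre/post measures, which is how the End Points section describes SF-8. A paired test within an arm asks whether that arm changed; it does not compare THEM with SOC. The Student t-test does compare them, but the plan does not say whether it is applied to the follow-up score or to the change from baseline. The first ignores the baseline score, and the second subtracts it with a fixed weight of 1 whatever its correlation with follow-up. Both arms supply a baseline SF-8, so precision that the trial has already paid for is left unused.

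The wording also leaves the choice of test and score open until the data are seen. At stake are the precision and clarity of one secondary comparison.

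**Working it through.** **1. The plan's own figure.** The only sample-size statement concerns the binary endpoint: 12% against 2%, two-sided 0.05, 80% power, 200 patients. The pooled two-proportion formula gives 102 per arm (204 in total), and 100 per arm has 79.6% power. The stated figure therefore reproduces. It says nothing about SF-8; only the 100 per arm is borrowed below.

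**2. Inputs for SF-8.** The documents give no SD, target difference or baseline-follow-up correlation r. Assumed: equal SDs at both times, and r = 0, 0.3, 0.5 or 0.7. Differences are in SD units.

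**3. Variance of the THEM-SOC difference, relative to a t-test on follow-up scores.** Follow-up t-test: 1. Change-score t-test: 2(1 - r). ANCOVA: 1 - r².

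| r | Change score | ANCOVA | ANCOVA / change = (1 + r)/2 |
|---|---|---|---|
| 0 | 2.00 | 1.00 | 0.50 |
| 0.3 | 1.40 | 0.91 | 0.65 |
| 0.5 | 1.00 | 0.75 | 0.75 |
| 0.7 | 0.60 | 0.51 | 0.85 |

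Below r = 0.5 the change score is less precise than the follow-up score alone.

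**4. Price of the covariate.** With N = 200, the variance rises by (N - 3)/(N - 4) = 197/196 = 1.005. ANCOVA breaks even with the follow-up t-test at r = √(1 - 196/197) = 0.07.

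**5. Detectable difference, 80% power, two-sided 0.05.** The noncentral t distribution gives 0.398 SD for the follow-up t-test with complete SF-8 in 100 per arm, and 0.446 SD with 80 per arm (80 is an assumption). Multiply by √(1 - r²) for ANCOVA and by √(2(1 - r)) for the change score.

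| r | Follow-up, 100 per arm | Change, 100 | ANCOVA, 100 | ANCOVA, 80 |
|---|---|---|---|---|
| 0.3 | 0.398 | 0.471 | 0.380 | 0.425 |
| 0.5 | 0.398 | 0.398 | 0.345 | 0.386 |
| 0.7 | 0.398 | 0.308 | 0.284 | 0.318 |

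**6. Why two paired tests cannot stand in for a comparison.** Suppose both arms change by the same true amount and each paired test has power p. One test is significant and the other is not with probability 2p(1 - p): 50% at p = 0.5 and 32% at p = 0.8. This would look like an arm difference where there is none.

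**7. Sensitivity to the timing of baseline.** Suppose knowledge of the arm shifts baseline answers in one arm by d and leaves follow-up unaffected. The bias is then r·d in size for ANCOVA, d for the change score and 0 for the follow-up t-test. With d = 0.1 SD (assumed), the ANCOVA bias is 0.03, 0.05 and 0.07 SD at r = 0.3, 0.5 and 0.7; the change-score bias is 0.10 SD.

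**8. Which follow-up score.** A visit at 2-4 weeks falls on days 14-28. If the visit window and the 30 days run from the same date, every visit on schedule precedes day 30 and triggers the call. The telephone score would then be the usual day-30 score.

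**The case against.** The best defense is that nothing here is an error. The Student t-test is the ordinary reading for a between-arm hypothesis, it is valid under randomization, the outcome is secondary, and no SF-8 power is claimed. The gain rests on an assumed correlation with surgery lying between the two scores; at r = 0.3 it is 0.398 - 0.380 = 0.018 SD. This stands: the point is an improvement and not a correction.

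A second objection is that ANCOVA could do harm if baseline answers are affected by the allocation. Under the assumed 0.1 SD shift, the bias of 0.03 SD at r = 0.3 exceeds the 0.018 SD gain, and at r = 0.5 the two are about equal (0.05 against 0.398 - 0.345 = 0.053). This also stands, and is why the recommendation is conditional.

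Some stronger readings are tempting, but the documents do not support them:

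- *Hypothesis 3 will be tested by paired tests within arms.* The sentence offers both tests and assigns neither to this hypothesis.
- *The baseline SF-8 is contaminated.* Both lists put randomization first, but neither gives times, and arm-specific material is handed over only after the procedure. The risk is possible, not documented.
- *Two follow-up SF-8 scores are planned and conflict.* The Schedule of Events shows one, and the call can be read as obtaining it at day 30. What is missing is a rule for when both exist.
- *All of hypothesis 3 is affected.* Satisfaction is measured only after surgery, so there is no baseline to adjust for.

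**Conclusion.** The point holds as a worthwhile, inexpensive improvement for the SF-8 part of hypothesis 3. The planned between-arm t-test is valid but generally less precise than the collected data allow; the paired t-test does not address the hypothesis. The variance reduction against a follow-up t-test is 9%, 25% or 49% at assumed correlations of 0.3, 0.5 or 0.7, and there is none at 0. These figures assume equal SDs and complete SF-8 data.

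The absence of any planned baseline adjustment is certain from the text; the size of the benefit is not. The benefit also depends on a baseline score that knowledge of the arm has not influenced, which the procedures do not now secure. A reader should not infer that the trial's main conclusions are at risk: the primary endpoints and the sample size do not depend on this choice.

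**What to change.** In Statistical Analysis, state the following for SF-8:

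- Day-30 PCS is compared between arms by ANCOVA with baseline PCS as covariate, and day-30 MCS likewise with baseline MCS. Each is reported as the adjusted THEM-SOC difference with 95% CI. Within-arm pre/post changes are descriptive, without p values.
- The day-30 score is the telephone score when the clinic visit precedes day 30. If the clinic score is used because the call failed, report the number of such patients by arm and repeat the analysis with day-30 scores only. The fallback mixes recovery times, and call completion could differ by arm.
- Report by arm the patients with no follow-up SF-8, including deaths.
- Give a rule for a missing baseline score (for example, the mean over both arms), so that patients with a follow-up score are not dropped. Say in advance which of PCS and MCS leads, or that both are secondary without a multiplicity claim.

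In Procedure, add one line: the baseline SF-8 is completed before the patient is told the allocation. If this cannot be assured, keep the Student t-test on the follow-up score as the main analysis and show ANCOVA as a sensitivity analysis.

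The cost is a short paragraph, a small change in the order of pre-treatment steps, and one degree of freedom per model. The planned SPSS software fits ANCOVA, and no new measurement is needed.

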6 cost, but the problem continues to escalate in many aspects. A recent report indicated
7 that Medicare expenditures were associated with a readmission rate estimated to be \$12
8 billion per year.¹ Another report² has indicated that about 24% of the entire Medicare
9 expenditure is consumed by readmissions. Ironically, those reports were based on data
10 gathered between 1974 to 1977, and definitely would be much higher in today
11 calculations according to current inflation index in GDP. As health care professionals,
12 we should be aware of all ongoing ramifications associated with readmissions, as the
13 integral scope of proper patient care is under scrutiny with all its related issues such as,
14 hospital reimbursement, physician credentialing process and regulation, referral pattern
15 and eventually educational enterprises.³
16

17 **Surgical Site Infections Following Arterial Revascularization with Groin Incision**
18
19

20 Vascular surgery especially arterial revascularizations with groin incisions
21 (ARGI) has always been associated with the potential of higher rates of readmission
22 pertaining to high-risk patients with multiple co-morbidities such as diabetes, cardiac
23 issues and poor general nutrition. These types of issues are more demanding in
24 geographical areas such as rural West Virginia where easy access to medical attention is
25 not available. In most cases, 30 day-readmissions are considered to be in-hospital
26 complications. However, some authorities have suggested that readmissions after
27 vascular interventions are really measures of post discharge complications rather than in-
28 hospital complications.³⁻⁸ Most U.S hospitals are currently in full compliance with the
29 Surgical Care Improvement Project (SCIP). Unfortunately, compliance with these
30 processes has not yet directly been associated with reduced SSI rates.^{9,10} In addition,
31 reports of 30-day readmission rates for vascular surgery patients are very high and it may
32 vary from 11 to 25%.^{1,8}
33

34 Identifying patients with higher rates of readmission after discharge is of essence
35 in order to pay more attention or even to deploy a system to monitor them closely. In one
36 study,¹¹ patients with a positive clinical culture obtained more than 48 hours after hospital
37 admission had an increased hazard of readmission (HR, 1.40; 95% CI, 1.33-1.46) after
38 adjusting for other co-morbidities. Another review indicated that SSIs may develop in

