39 10% of the 3,663 patients who underwent an inpatient general surgical procedure. It has
40 been reported that diagnosis of SSI after discharge was also associated with a high
41 readmission rate despite occurring in healthier patients. It has been proposed that
42 discharge specific instructions related to wound infections along with a wound
43 surveillance in-clinic visit within the first week may result in a decreased readmission
44 rate.⁷ Gohil et al assessed 30-day readmission rates from 323 hospitals and reported that
45 infection-related readmissions accounted for 28% of all readmissions. The same study
46 reported that academic hospitals had higher all-cause and infection-related readmission

1 rates.¹²

2
3 The thought of reducing readmission and infection rates has been energized by the
4 recent policy proposals suggested by the Medicare Payment Advisory Commission to
5 lower average per-case reimbursements to hospitals with high (risk-adjusted) rates of re-
6 hospitalizations. It is important to identify high-risk patients in order to be more focused
7 and to incorporate procedures to identify early signs of infection. This approach of
8 increased outpatient support has been proven to be cost effective.² Some researchers have
9 developed a scoring system to accurately identify patients at high risk for 30-day
10 unplanned readmissions and suggested this could help direct discharge and home health
11 care resources to patients, which ultimately could be used to reduce readmissions and
12 improving efficiency.⁸ Gibson et al reported that diagnosis of surgical site infection (SSI)
13 after discharge is associated with a high readmission rate despite occurring in healthier
14 patients.⁷ The authors of a recent study reported that female gender, obesity, diabetes,
15 smoking, hypertension, coronary artery disease, critical limb ischemia, chronic
16 obstructive pulmonary disease, dyspnea, and neurologic disease were all of among
17 significant predictors of SSI after vascular reconstruction was performed.¹³ Another
18 important potential impact of telehealth technology is that it may minimize the burden
19 and cost of 3rd party home visits to evaluate wounds or provide treatment. Currently,
20 many interventions of vascular surgery require postoperative visiting nursing service
21 (VNS) to evaluate wound or treatment at home. The home visit approach utilizes

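### The primary endpoint is stated in ways that do not agree, no rule says which version decides, and the 80% power is not clearly tied to any of them

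*Combined protocol and SAP*

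**What the plan says.** All places are in the combined protocol and SAP.

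- **Outcomes and End Points** give the same list of three: "The primary outcomes include 30-day readmissions, post-operative complications and access site/wound infections".
- **Study hypotheses** treat two of these separately: "A smaller percentage of THEM patients will require a 30-day unplanned" readmission, and "A smaller percentage of THEM patients will develop a SSI". None concerns complications as such.
- **Study Design** measures the primary endpoints (plural) as one 0/1 variable: any unplanned 30-day readmission and/or complication.
- **Sample Size** gives 200 subjects 80% power at two-sided 0.05 for a 30-day infection/readmission rate of about 12% against about 2%, with 220 enrolled to allow for 10% drop-out. The estimate is said to rest on readmission rates from an earlier study.
- **Definitions** describe event-free survival as freedom from unplanned 30-day readmission and/or access-site wound infection. This is not labelled primary.
- **Statistical Analysis** allows chi-square or Fisher for categorical variables as deemed appropriate, compares freedom-from-event curves by log-rank, and calls any two-sided p below 0.05 significant.

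**The concern.** The primary endpoint decides whether the trial has succeeded, and here at least two different things carry that label. Readmission, complications, infection or a composite could each be presented as the primary result once the data are known, and chi-square, Fisher or log-rank could each be presented as the test. The trial is open-label. Blinded endpoint assessment protects the classification of events, but not the choice of which endpoint is called primary.

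Two things are at stake. One is the false-positive rate, if a significant result on any one listed outcome is taken as success. The other is power: the stated 80% belongs to an endpoint with rates of 12% and 2%, and the plan does not clearly say which endpoint that is.

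**Working it through.** **1. Reproduce the stated sample size.** Inputs from Sample Size: 12% and 2%, two-sided 0.05, 80% power, equal arms. The mean rate is 0.07. With pooled variance under the null:

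n per arm = [1.960 × √(2 × 0.07 × 0.93) + 0.842 × √(0.12 × 0.88 + 0.02 × 0.98)]² / 0.10² = (0.707 + 0.298)² / 0.01 ≈ 101.01, rounded up to 102.

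The plan has 100 per arm. Power at 100 is Φ[(0.10 × √100 − 0.707) / 0.354] = Φ(0.827) = 79.6%. The plan's figure is reproduced. With 110 enrolled per arm and 10% lost, 99 remain.

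**2. Exact power at 12% versus 2%, 100 per arm** (enumerating all binomial outcomes):

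| Test | Power |
|---|---|
| Chi-square, uncorrected | 83.7% |
| Chi-square, switching to Fisher if an expected count is below 5 | 82.4% |
| Fisher alone | 76.2% |

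The choice of test moves power across the stated 80%.

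**3. Which endpoint do 12% and 2% describe?**

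- *Slash read as a composite:* readmission and/or infection is none of the three listed outcomes. It is narrower than the Study Design variable, because it leaves out non-infectious complications. It resembles only the event-free-survival definition.
- *Slash read as each rate separately:* it matches two of the three listed outcomes and hypotheses 1 and 2. There is then more than one primary test, and multiplicity is explicit.
- *Readmission alone:* the stated source is readmission rates, and the Background says that "reports of 30-day readmission rates for vascular surgery patients are very high and it may" "vary from 11 to 25" percent, so 12% is also plausible for readmission by itself.

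The text does not choose among these. It gives no rates for the Study Design composite, so power for that endpoint is unknown.

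**4. False claims of benefit under each possible success rule.** The nominal rate in the benefit direction is 0.05 / 2 = 2.5%. The documents give no complication rate and no overlap between outcomes, so both are assumed. The simulations have 100 per arm and no treatment effect.

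| Rule and assumptions | Chi-square | Fisher |
|---|---|---|
| Any of three: readmission 12%, complications 15-25%, infection 8-10% counted within complications, 50-100% of readmissions arising from complications | 5.1-6.8% | 3.1-4.2% |
| Any of three: readmission set so that readmission-or-infection is 12%; infection 4-8% | 5.5-6.8% | 3.0-4.0% |
| Any of three: infection nested in complications, a different dependence model | 5.4-6.9% | 3.2-4.2% |
| Any of three: independent or weakly correlated | 7.0-7.6% | 4.1-5.1% |
| One named outcome, event rate 10-20% | about 2.6% | 1.4-1.6% |

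As a check on the weak-overlap row, three independent tests at exactly 2.5% give 1 − 0.975³ = 7.3%. Chi-square runs slightly above nominal at these sizes, which explains values up to 7.6%.

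If one composite decides, the two-sided error by chi-square is 4.9-5.3% against 5%. If all three outcomes must be significant, it is at most 1.4% when there is no effect on any of them. Neither rule inflates the error.

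**The case against.** The best defence is that Study Design holds the only operational definition, a single 0/1, and that a wound infection is itself a post-operative complication. The list in Outcomes and End Points would then name the components of one composite, with no inflation from this source. That reading is available, but the plan does not secure it. End Points repeats the list without a composite, the hypotheses separate readmission from infection, and the powered quantity omits non-infectious complications. Even on this reading the stated power is not tied to the deciding endpoint.

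Four stronger readings are tempting and not supported.

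- A reader might infer that the trial's false-positive rate *is* 5-7%. No section says that any one outcome may carry the claim. What is shown is ambiguity, with an illustrated consequence under one rule.
- A reader might infer that the powered quantity matches nothing labelled primary. That holds only if the slash denotes a composite.
- A reader might build a composite rate from Background figures, such as an infection rate of "10% of the 3,663 patients who underwent an inpatient general surgical procedure" and the finding that "infection-related readmissions accounted for 28% of all readmissions". The first comes from general surgery. The second covers infection-related readmissions across 323 hospitals, not groin wounds. They cannot be combined into a rate for this trial.
- A reader might call the choice between chi-square and Fisher wholly open. The wording is loose but conventional. At 12% versus 2% the expected count is 100 × 0.07 = 7 events per arm, and the usual rule would give chi-square. The point that stands is that the rule is unstated and that log-rank remains a rival test for event-free survival.

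**Conclusion.** The concern holds and should be fixed before outcomes are examined by arm. The documents establish the inconsistency directly: two different specifications are called primary, the power statement uses a third wording, and there is no deciding outcome, any-or-all rule or testing order. The sample-size arithmetic is sound for its own inputs; the defect is that the endpoint it serves is unclear.

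The size of the inflation is conditional. It is absent if one composite decides or if all three outcomes must be significant. If any one suffices, overlapping outcomes give roughly two to three times the nominal 2.5% by chi-square, and somewhat above nominal by Fisher. Those figures rest on assumed event rates and overlap and are not limits. The exact power figures rest only on the plan's 12%, 2% and 100 per arm.

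**What to change.** Before outcomes are examined by arm, amend the plan as follows.

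1. Name one deciding primary endpoint and use identical wording in Outcomes, Study Design, Sample Size, End Points and Definitions. The choice is the sponsor's. Unplanned readmission and/or access-site wound infection best fits the Sample Size wording and the event-free-survival definition.
2. Name one deciding test at two-sided 0.05: chi-square, or chi-square with a pre-set switch to Fisher when an expected count is below 5. State that the log-rank comparison is supportive.
3. Use the qualifier unplanned consistently; the primary list omits it, while Study Design and hypothesis 1 include it.
4. If complications form part of the endpoint, state which events count and how they relate to stroke, MI and death, which are listed as secondary.
5. Make the other listed outcomes secondary, or test them in a fixed order at 0.05, each only if the one before is significant.
6. State which endpoint the 12% and 2% describe, and restate power if a different endpoint is chosen.

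The cost is a text amendment with no new outcome. Outcomes moved out of the primary endpoint lose confirmatory status, and under a fixed order a non-significant result ends confirmatory testing of those that follow. The 200 evaluable subjects stand only if the sponsor confirms that 12% and 2% describe the chosen endpoint; otherwise power must be restated and the sample size may change.
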